6.3 SUMMARIES OF CONDUCT OF STUDY

Enrollment, major protocol violations, and discontinuations from the study will be listed. The incidence of treatment discontinuation for reasons other than disease progression will be tabulated.

Data related to the administration of study treatment components will be listed, and any dose modifications will be flagged. The number of doses, treatment cycles, average dose received, and relative dose intensity for each treatment component will be summarized using descriptive statistics (mean, standard deviation, median, and range).

6.4 SUMMARIES OF DEMOGRAPHIC AND BASELINE CHARACTERISTICS

Demographic and baseline characteristics by treatment group, such as age, sex, race, and duration of malignancy, will be summarized using descriptive statistics (mean,

standard deviation, median, and range) for continuous variables and frequencies and percentages for categorical variables.

6.5 SAFETY ANALYSES

The safety analyses will be performed by treatment group, separately for each study phase (i.e., dose-escalation and expansion). The main analysis for safety will include data until end of study. Additionally, a censoring will be applied as of 1 March 2018 to the safety analyses, to evaluate the effect of the triplet drug combination in each treatment group. The sensitivity analysis will be based on the censored safety dataset and will include data from patients as of 1 March 2018 plus the 90-day safety reporting window (see Section 5.3.1). Patients enrolled and who have not received any treatment with atezolizumab will be analyzed separately by treatment group, G +Pola and R +Pola.

Safety will be assessed through summaries of adverse events, changes from baseline in laboratory test results, and laboratory data with values outside of the normal ranges.

All adverse events occurring on or after the first dose of study treatment will be summarized by mapped term, appropriate thesaurus levels, and NCI CTCAE v4.0 grade. All SAEs, adverse events of special interest, and selected adverse events will be summarized and listed.

Deaths reported during the treatment period and during post-treatment follow-up will be listed.

Relevant laboratory results will be displayed by time, with Grade 3 and 4 values identified as appropriate.

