5.3.1 Adverse Event Reporting Period

Investigators will seek information on adverse events at each patient contact. All adverse events, whether reported by the patient or noted by study personnel, will be recorded in the patient's medical record and on the Adverse Event eCRF.

After informed consent has been obtained **but prior to initiation of study treatment**, only SAEs caused by a protocol-mandated intervention (e.g., invasive procedures such as biopsies, discontinuation of medications) should be reported (see Section 5.4.2 for instructions for reporting SAEs).

After initiation of study treatment, all adverse events will be reported until 90 days after the last dose of study treatment. After this period, the investigator should report any SAEs that are believed to be related to prior study treatment (see Section 5.6).

An exception is made for Grade 3 or 4 infections (related and unrelated to study treatment), which should be reported until up to 2 years after the last dose of obinutuzumab (G+Atezo+ Pola treatment group).

Similarly, second malignancies (related and unrelated to study treatment) will be reported indefinitely (even if the study has been closed) for patients who received obinutuzumab (see Section 5.6).

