5.6 ADVERSE EVENTS THAT OCCUR AFTER THE ADVERSE EVENT REPORTING PERIOD

After the end of the adverse event reporting period (defined as 90 days after the last dose of study treatment), all deaths, regardless of cause, should be reported through use of the Long-Term Survival Follow-Up eCRF.

In addition, if the investigator becomes aware of a serious adverse event that is believed to be related to prior exposure to study drug, the event should be reported through use of the Adverse Event eCRF.

An exception is made for Grade 3 and 4 infections (related and unrelated to prior study treatment), which should be reported until up to 2 years after the last dose of study treatment.

The Sponsor should also be notified of events of second malignancies indefinitely (related and unrelated to study treatment, even if the G+Atezo+pol treatment group or the overall study has been closed) for patients who received obinutuzumab.

If the EDC system is not available, the investigator should report these events directly to the Sponsor or its designee, either by faxing or by scanning and emailing the paper

Clinical Trial Serious Adverse Event/Adverse Event of Special Interest Reporting Form using the fax number or email address provided to investigators.

**5.7 EXPEDITED REPORTING TO HEALTH AUTHORITIES,
INVESTIGATORS, INSTITUTIONAL REVIEW BOARDS, AND
ETHICS COMMITTEES**

The Sponsor will promptly evaluate all SAEs and adverse events of special interest against cumulative product experience to identify and expeditiously communicate possible new safety findings to investigators, IRBs, ECs, and applicable health authorities based on applicable legislation.

To determine reporting requirements for single adverse event cases, the Sponsor will assess the expectedness of these events using the following reference document:

- Obinutuzumab Investigator's Brochure
- Atezolizumab Investigator's Brochure
- Polatuzumab Vedotin Investigator's Brochure
- Rituximab Investigator's Brochure

The Sponsor will compare the severity of each event and the cumulative event frequency reported for the study with the severity and frequency reported in the applicable reference document.

Reporting requirements will also be based on the investigator's assessment of causality and seriousness, with allowance for upgrading by the Sponsor as needed.

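### Section 6.5 tabulates adverse events to the trial-level end of study, although complete collection stops 90 days after each patient's last dose, so the frequency tables mix complete and selective follow-up

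*Combined protocol and SAP*

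**What the plan says.** **Analysis rule.** Section 6.5 says "The main analysis for safety will include data until end of study". It adds that "All adverse events occurring on or after the first dose of study treatment will be summarized by mapped term", by thesaurus level and by CTCAE grade. Serious events, events of special interest and selected events are to be summarized and listed; deaths are listed only. No closing date is set for the individual patient. The sensitivity analysis cuts at 1 March 2018 plus the 90-day window, which is a calendar date.

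**Collection rule.** Section 5.3.1 says "After initiation of study treatment, all adverse events will be reported until 90 days after the last dose of study treatment". Section 5.4.2.2 and the adverse event footnotes of Appendices 1 and 2 agree. Then: "After this period, the investigator should report any SAEs that are believed to be related to prior study treatment". Section 5.6 makes this conditional on the investigator becoming aware of the event, and directs that "the event should be reported through use of the Adverse Event eCRF", the same form as is used on treatment.

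**Exceptions.** Grade 3-4 infections and, for patients who received obinutuzumab, second malignancies continue to be reported whether related or not. For infections, Section 5.3.1 says "which should be reported until up to 2 years after the last dose of obinutuzumab (G+Atezo+ Pola treatment group"; Section 5.6 says "which should be reported until up to 2 years after the last dose of study treatment", with no restriction to obinutuzumab. Late deaths from any cause go on a separate survival form.

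**End of study.** Section 3.2 ties it to the 90-day visit of the last remaining patient, so it is one date for the whole trial.

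**The concern.** A frequency table is read as the proportion of patients who had an event over a period in which any such event would have been recorded. Here that is true only up to 90 days after last dose. After that, a Grade 2 event or an unrelated serious event (outside the exceptions) is not collected, while a related serious event or a Grade 3-4 infection is. The late part therefore adds to the serious and severe rows and little else. How much late time a patient contributes depends on how early treatment stopped relative to the trial's end.

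Safety is a stated objective, including how often and when events occur (Section 2.1), and a safety signal stopped enrollment (Section 1.5.1). These tables are a main product of the study.

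**Working it through.** The plan gives no figure to reproduce. The check is a comparison of rules followed by day counts.

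**1. What is collected, by period**

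| Event type | First dose to last dose + 90 days | Later | Enters the Section 6.5 tables |
|---|---|---|---|
| Non-serious events (outside the exceptions below) | All | Not collected | Yes |
| Serious, related | All | If the investigator learns of it; no end date | Yes |
| Serious, unrelated (outside the exceptions below) | All | Not collected | Yes |
| Grade 3-4 infections | All | To 2 years, any cause; 5.3.1 and 5.6 differ on which patients | Yes |
| Second malignancies | All | After obinutuzumab, indefinitely, any cause | Yes |
| Deaths | All | All, on a separate form | Listed only |

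**2. Length of the selective period**

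Inputs: 21-day cycles; maintenance from 8 weeks after Day 1 of Cycle 6, every 2 months for up to 24 months of 28 days (Section 3.1.2.1.2, Table 2); DLBCL induction only since Version 7 (Section 3.1.3.1). Count Day 1 of Cycle 1 as day 0.

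- Day 1 of Cycle 6: 5 × 21 = 105.
- Maintenance start: 105 + 56 = 161.
- Twelfth and last obinutuzumab dose (Month 23): 161 + 11 × 56 = 777.
- 90-day visit of an FL completer, taken as the study end: 777 + 90 = 867.

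| Patient with the same start date | Complete collection ends | Selective days | Share of 867 |
|---|---|---|---|
| DLBCL, 6 cycles | 105 + 90 = 195 | 867 − 195 = 672 | 78% |
| DLBCL or FL, 2 cycles | 21 + 90 = 111 | 867 − 111 = 756 | 87% |
| FL, full maintenance | 777 + 90 = 867 | 0 | 0% |

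The selective figures are ceilings: they require the patient to be alive and followed to day 867.

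The survival follow-up footnotes of Appendices 1 and 2 define the study end differently, requiring at least 1 year of DLBCL follow-up after treatment. Taken from last dose, that alone leaves 365 − 90 = 275 selective days for a surviving DLBCL patient. Under either definition there is three-monthly contact after treatment through which late events can reach the investigator.

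**3. Does the sensitivity analysis remove the mix?**

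For a patient whose last dose was x days before 1 March 2018, complete collection ends at 1 March 2018 − x + 90 days, and the dataset closes at 1 March 2018 + 90 days. The difference is x selective days, for example 180 if x = 180. It does not.

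**4. Granularity of the tables**

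Section 6.5 separates the phases. From Section 6.1, the expansion phase holds 13 − 9 = 4 FL and 23 − 7 = 16 DLBCL patients, if all enrolled are counted. One patient counted for a term only because of a late event moves its rate by 1/4 = 25 or 1/16 = 6.25 percentage points. If FL patients at the RP2D are pooled as in Section 6.2 (4 + 6 = 10), the step is 10 points. This is the step size, not an estimate of bias.

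**The case against.** The strongest case on the other side is that these are descriptive tables in a non-randomized study of 36 enrolled patients. No exposure-adjusted rate and no comparison of FL with DLBCL is planned, so no formal inference is harmed. Late related serious events are real, and taking them out of the headline tables of a study halted for an immune-mediated signal has a cost. Most late categories are already listed individually under Section 6.5. All of this stands. It bears on the importance of the point and on how late events should be displayed, but it does not supply a per-patient limit.

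Some stronger readings are tempting but not supported:

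- *Every late serious event is related by rule, so treatment-related percentages are inflated.* Grade 3-4 infections and second malignancies are reported regardless of cause, and many would be serious. Section 6.5 also plans no table by relatedness.
- *Infections in FL have the longest window.* They stop at 2 years; second malignancies after obinutuzumab and related serious events have no end date.
- *672 or 756 days measures the bias.* They measure calendar time under favorable follow-up. In relapsed or refractory DLBCL the documents quote median PFS of 5.6 months (rituximab plus polatuzumab vedotin at 2.4 mg/kg) and 1.9 months (obinutuzumab plus polatuzumab vedotin) in Section 1.5.4.3, so many patients may be followed for less time.
- *The tables overstate risk.* Counting a late event does not overstate the proportion ever affected; the uncollected late events make that proportion too low. What is distorted is the mix of serious and non-serious events, and of severe and mild ones.

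**Conclusion.** The point holds as a reporting-window flaw in the descriptive safety tables. Section 6.5 has no per-patient upper limit. Neither the trial-level study end nor the calendar cut of the sensitivity analysis supplies one. The tables for adverse events, serious events, events of special interest and selected events therefore mix complete and selective collection, and the selective share runs from none for an FL patient who completes maintenance to a ceiling of 78% or 87% of follow-up in the DLBCL examples. Those ceilings assume a common start date, a study end set by an FL completer, and a patient alive and followed to that date. The effect on any event rate cannot be computed, because the documents give no late event rates. The primary efficacy analysis is unaffected. Separately, Sections 5.3.1 and 5.6 contradict each other on whose late infections are reported.

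**What to change.** Add to Section 6.5: frequency tables for adverse events, serious adverse events, events of special interest and selected events include events with onset from first dose to 90 days after the patient's last dose of study treatment. Apply the same limit within the dataset censored at 1 March 2018. Summarize and list later related serious events, Grade 3-4 infections and second malignancies separately, labelled as selectively collected, and keep the existing listing of deaths. Reconcile Sections 5.3.1 and 5.6 on late infections, since that decides which patients the separate display covers.

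The cost is a short addition to the text and one date flag per event; no new data are needed and no event is lost. The downside is that late events leave the headline tables, so the separate display should be cross-referenced from them.

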2.1 SAFETY OBJECTIVE

The safety objectives for this study are as follows:

- To determine the recommended Phase II dose (RP2D) for polatuzumab vedotin when given in combination with fixed doses of obinutuzumab and atezolizumab on the basis of the following endpoint:

Incidence of DLTs during Cycles 1 and 2 of study treatment:

- To evaluate the safety and tolerability of the G+Atezo+Pola treatment group and the R+Atezo+Pola treatment group on the basis of the following endpoints:
 - Nature, frequency, severity, and timing of adverse events
 - Changes in clinical laboratory results during and following study treatment administration

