4.3.2.6 Post-Induction Treatment

Patients with FL who achieve a CR, a PR, or stable disease at EOI will receive maintenance treatment with obinutuzumab for 24 months, as outlined in [Table 8](#).

Maintenance treatment should start 8 weeks (\pm 1 week) after Day 1 of Cycle 6 and will continue until disease progression or unacceptable toxicity for up to 24 months.

Table 8 Maintenance Treatment for Patients with Follicular Lymphoma

Treatment	Dose	Route	Regimen (Months 1–24)
Obinutuzumab	1000 mg	IV	Day 1 of every other month (i.e., every 2 months), starting with Month 1

FL=follicular lymphoma; IV=intravenous.

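### Triplet safety is isolated only in a sensitivity dataset cut at one calendar date; a per-patient window built from the atezolizumab doses would classify events by actual exposure

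*Combined protocol and SAP*

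**What the plan says.** The safety objective in Section 2.1 is "To evaluate the safety and tolerability of the G+Atezo+Pola treatment group and the R+Atezo+Pola treatment group". For this, Section 6.5 sets out three analyses.

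- **Main analysis.** "The main analysis for safety will include data until end of study".
- **Triplet evaluation.** "a censoring will be applied as of 1 March 2018 to the safety analyses, to evaluate the effect of the triplet drug combination". This dataset "will include data from patients as of 1 March 2018 plus the 90-day safety reporting window", and the section calls the result a sensitivity analysis.
- **Never exposed.** "Patients enrolled and who have not received any treatment with atezolizumab will be analyzed separately by treatment group", as G+Pola and R+Pola.

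Presentation is also fixed: "The safety analyses will be performed by treatment group, separately for each study phase". Under Section 6.2, one dose of each component places a patient in the primary population. No rule there or in Section 6.5 ends a patient's triplet time when atezolizumab ends.

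Treatment went on without atezolizumab after the 1 March 2018 letter. Tables 3 and 4 give G+Pola and R+Pola induction, still under the triplet headings. Under Section 4.3.2.6, FL patients with at least stable disease "will receive maintenance treatment with obinutuzumab for 24 months".

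**The concern.** A treatment group's AE table should let the reader tell which regimen the patient was on when the event began. The main analysis does not. Once a patient has had one atezolizumab dose, everything that follows is tabulated under the triplet group name, including months on obinutuzumab alone. Section 6.5 specifies event summaries and no exposure-adjusted rates, so this extra time can only add patients with events to the incidence column.

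The dataset meant to isolate the triplet uses a date that belongs to the study and not to the patient. Sections 4.6.2 and 5.1.7 (Tables 11 and 14) allow atezolizumab to stop while other drugs continue. The 90-day window in Section 5.3.1 does not correct for this, because it runs from the last dose of study treatment, which Section 2 defines as all components together.

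Section 6.6 handles the same problem differently for efficacy. There the censored dataset is the analysis; in Section 6.5 it is only a sensitivity analysis.

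**Working it through.** The plan states no figure to reproduce. The check is date arithmetic on the protocol's own schedule.

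**Inputs**
- Six 21-day induction cycles. With Day 1 of Cycle 1 as day 0, Day 1 of Cycle 6 is 5 × 21 = day 105.
- Atezolizumab in induction on Day 1 of Cycles 2–6 (Section 4.3.2.2): days 21, 42, 63, 84 and 105. Cycle 1 contains none.
- FL maintenance starts 8 weeks after Day 1 of Cycle 6 (Section 4.3.2.6): 105 + 56 = day 161.
- Obinutuzumab every other month from Month 1, with a month of 28 days (Table 2). The last dose, in Month 23, is at 161 + 22 × 28 = day 777.
- DLBCL after the letter: R+Pola to Cycle 6 and no consolidation (Section 3.1.3.1). The last dose is at day 105.
- AE reporting to 90 days after the last study treatment (Section 5.3.1). The exceptions for later infections, related serious events and second malignancies are left out.

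**Main analysis**

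Let E = last dose of any component + 90, and A = last atezolizumab dose + 90. The time beyond the atezolizumab window is E − A, and its share is (E − A)/E. For FL, E = 777 + 90 = 867. For DLBCL, E = 105 + 90 = 195.

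| Patient completing the remaining treatment | Last atezolizumab | A | E − A | Share |
|---|---|---|---|---|
| FL, one dose | 21 | 111 | 756 | 87% |
| FL, all five induction doses, none later | 105 | 195 | 672 | 78% |
| FL, last dose in maintenance Month 12 | 161 + 11 × 28 = 469 | 559 | 308 | 36% |
| DLBCL, one dose | 21 | 111 | 84 | 43% |
| DLBCL, three doses | 63 | 153 | 42 | 22% |
| DLBCL, five doses | 105 | 195 | 0 | 0% |

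**Calendar cut**

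1 March 2018 + 90 days is 30 May 2018. Let g be the days from a patient's last atezolizumab dose to 1 March 2018. The calendar rule runs g days longer than a per-patient rule for a patient still on other drugs.
- Dosing on schedule in induction (every 21 days): g = 0 to 20.
- Dosing on schedule in maintenance (every 28 days): g = 0 to 27.
- An FL patient in the 56-day interval between Cycle 6 and maintenance on that date: g up to 55.
- Atezolizumab stopped earlier with other drugs continued: g is whatever the gap was. Assumed gaps of 60, 90 and 180 days give 60, 90 and 180 extra days.

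The documents give neither g nor the number of such patients.

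**The case against.** The strongest case is that the plan already makes the separation. It assigns the triplet effect to the censored dataset, takes out the never-exposed patients, and reports a full-follow-up summary that suits an objective worded by treatment group. That stands. A reader might infer that Section 6.5 passes off atezolizumab-free exposure as the triplet's safety profile; the text does not say so.

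A reader might also infer that neither dataset characterises the signal that stopped the trial. The documents do not support this. The two FL cases prompted the 1 March 2018 letter (Section 1.5.1), so they precede the cut and lie inside the censored dataset. Serious events and events of special interest are listed, dosing is listed by component (Section 6.3), and causality is judged for each drug (Section 5.3.4). Individual cases can therefore be matched to exposure. The incidence tables cannot.

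Three limits also stand.
- The percentages above are shares of one patient's follow-up, not of events.
- Ninety days is a convention. Appendices 3 and 4 sample atezolizumab at 120 ± 30 days after the last dose, and Section 4.4.2 restricts live vaccines for five months after discontinuation, so later time is not necessarily free of the drug's influence.
- Maintenance with G+Atezo contains no polatuzumab vedotin, so a window built on atezolizumab doses marks atezolizumab exposure and not all three drugs at once.

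**Conclusion.** The point holds as a cheap improvement. The main analysis can carry a large amount of atezolizumab-free follow-up under the triplet labels: up to 78–87% of an FL patient's AE data when no atezolizumab was given in maintenance, and up to 43% of a DLBCL patient's. These are upper cases. They assume on-time dosing and completion of all remaining treatment, and the documents do not say how many patients fit them.

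The defect in the censored dataset is narrower. For patients being dosed on schedule at 1 March 2018 the calendar date is a close stand-in for a per-patient date. The rule fails for earlier stoppers who stayed on other drugs. That failure is real in the rule and of unknown size.

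Small groups make single misclassified patients visible. Section 6.1 gives 13 FL patients enrolled, 9 of them in dose escalation, which leaves 13 − 9 = 4 in expansion. If phases are kept apart, one patient moves an expansion-phase incidence by 1/4 = 25 percentage points.

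**What to change.** In Section 6.5:

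1. Keep the end-of-study analysis and describe it as the overall safety summary of the study as conducted.
2. For the analysis of the triplet effect, replace the single calendar date with a per-patient atezolizumab-exposed period, from first atezolizumab dose to last atezolizumab dose + 90 days.
3. Tabulate events before that period (Cycle 1) and after it separately, with patient-time for each period.
4. Keep the separate analysis of patients who never received atezolizumab.

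The cost is one derived date per patient, from dosing data that Section 6.3 already lists by component, and one more table split. No treatment or data collection changes. The downside is that the 90-day limit may place some late immune events in the later period; they remain visible in the end-of-study summary.

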4.4.2 Prohibited Therapy

Use of the following therapies (excluding protocol-specified treatments) is prohibited during the study:

- Any anti-cancer therapy, approved or investigational, other than intrathecal CNS prophylaxis
- Hormonal therapy other than contraceptives, stable hormone replacement therapy, or megestrol acetate
- Biologic agents other than hematopoietic growth factors (as described in Section 4.3.2.7)
- Immunostimulatory agents, including, but not limited to, IFN- α , IFN- γ , or IL-2
 - Immunostimulatory agents, in combination with atezolizumab, could potentially increase the risk for autoimmune conditions. Patients should not receive other immunostimulatory agents for 10 weeks after the last dose of atezolizumab.
- Vaccines, as outlined below:
 - Any live, attenuated vaccine (e.g., FluMist[®]) is prohibited while the patient is receiving atezolizumab and for a period of five months after discontinuation of atezolizumab. Inactivated influenza vaccines are allowed only during flu season.
 - Vaccination with live vaccines is not recommended during treatment with obinutuzumab and until B-cell recovery.

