5.3.4 Assessment of Causality of Adverse Events

Investigators should use their knowledge of the patient, the circumstances surrounding the event, and an evaluation of any potential alternative causes to determine whether an adverse event is considered to be related to any of the study treatment components, indicating "yes" or "no" accordingly. The following guidance should be taken into consideration:

- Temporal relationship of event onset to the initiation of study treatment
- Course of the event, considering especially the effects of study treatment modifications or discontinuation, or reintroduction of study treatment (as applicable)
- Known association of the event with the study treatment or with similar treatments
- Known association of the event with the disease under study
- Presence of risk factors in the patient or use of concomitant medications known to increase the occurrence of the event
- Presence of non-treatment related factors that are known to be associated with the occurrence of the event

For patients receiving combination therapy, causality will be assessed individually for each protocol-mandated therapy.

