- ee Includes CT scan of the neck (if clinically indicated), chest, abdomen, and pelvis. If contrast is medically contraindicated (e.g., patients with contrast allergy or impaired renal clearance), MRI scans of the chest, abdomen, and pelvis (and neck, if clinically indicated) and a non-contrast CT scan of the chest may be performed. Combined PET/CT scanners may be used to collect diagnostic CT scans, but only according to the technical guidelines in the imaging manual. The screening CT scan must be performed within 35 days prior to Day 1 of Cycle 1.

Appendix 1

Schedule of Assessments for Patients with Follicular Lymphoma (cont.)

- ^{ff} Perform within 7 days prior to Day 1 of Cycle 3, and at 12, 18, and 24 months after initiation of induction treatment, within 14 days prior to treatment administration. Patients with radiographic evidence of progression at the end of Cycle 2 who continue to receive study treatment per criteria defined in Section 3.1.1 should have a CT scan repeated 4–8 weeks later.
- ^{gg} Perform only if not done within the previous 3 months.
- ^{hh} Bone marrow biopsy and aspirate must be performed within approximately 3 months prior to Day 1 of Cycle 1.
- ⁱⁱ For patients with bone marrow involvement at screening, a repeat assessment will be performed at EOI if there is radiologic evidence of a complete response, and during maintenance or at EOM if there is radiologic evidence of a complete response or if clinically indicated (e.g., if there is clinical suspicion of progressive disease in the bone marrow with no radiologic evidence of progression).
- ^{jj} Refer to Sections 4.3.2.5 and Section 4.3.2 for details on dosing and schedule.
- ^{kk} *Patients who experience disease progression or discontinued study treatment will be evaluated for survival status and new anti-lymphoma treatment every 3 months until the end of the study. The end of the study is defined as the time when all enrolled patients with FL have completed or discontinued study treatment and all enrolled patients with DLBCL have been followed for at least 1 year after they have completed or discontinued study treatment.*

Appendix 2
Schedule of Assessments for Patients with Diffuse Large B-Cell Lymphoma

	Screening ^a		Induction (6 months; 21-day cycles)		EOI After Last Induction Dose ^b	90-Day Safety FU Visit (at 3 Months) ^c	Survival FU Period (Q3M) ^{ee}
	D -28 to D -1	D -14 to D -1	Cycle 1 (\pm 1 day)	Cycles 2–6 (\pm 2 days)			
			D1	D1			

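### Section 6.5 does not separate adverse events that begin after new anti-lymphoma treatment, so next-line events are mixed into the all-cause safety tables, including the 1 March 2018 analysis meant to evaluate the triplet

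*Combined protocol and SAP*

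**What the plan says.** - **What is tabulated.** Section 6.5: "All adverse events occurring on or after the first dose of study treatment will be summarized by mapped term". The tables are by treatment group and separate for each study phase. The section gives no end to the counting period for an individual patient and plans no summary of treatment-related events.
- **What is collected.** Section 5.3.1: "After initiation of study treatment, all adverse events will be reported until 90 days after the last dose of study treatment". Section 5.4.2.2 and the adverse event footnotes of Appendices 1 and 2 repeat the rule. In the obinutuzumab group, Grade 3 or 4 infections, related or not, are an exception, "which should be reported until up to 2 years after the last dose of obinutuzumab".
- **Data cuts.** "The main analysis for safety will include data until end of study". A sensitivity analysis is censored at 1 March 2018 plus the 90-day reporting window. That censoring is applied "to the safety analyses, to evaluate the effect of the triplet drug combination in each treatment group".
- **New treatment.** It appears as a follow-up data item. Under Appendix 1 footnote kk and Appendix 2 footnote ee, patients who progress or stop study treatment "will be evaluated for survival status and new anti-lymphoma treatment every 3 months until the end of the study".

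**The concern.** The nature, frequency, severity and timing of adverse events are the safety endpoints in Section 2.1. A patient with relapsed or refractory lymphoma who progresses may start another regimen well before 90 days have passed. Cytopenias, febrile neutropenia and infections on that regimen are the same kinds of event that the study drugs cause, so an all-cause table cannot tell them apart. The mixing can only raise an incidence, and there is no control arm against which to judge it.

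It matters most for the 1 March 2018 analysis. That dataset is meant to isolate the triplet, but its cut is a calendar date. It removes events after the cut and leaves in any next-line event that falls before it.

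**Working it through.** No figure in the plan needs reproducing; the check is of the text, followed by scale.

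**1. The rules side by side.** Counting starts at first dose (6.5). Collection ends 90 days after last dose (5.3.1, 5.4.2.2, Appendix 1 footnote aa, Appendix 2 footnote w), or at 2 years for Grade 3 or 4 infections after obinutuzumab. The data cut is end of study, or 1 March 2018 plus 90 days, which is 30 May 2018 if counted from that date. The start of new anti-lymphoma treatment ends or divides none of these periods.

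**2. Can next-line treatment fall inside the window?** Progression is a reason for permanent discontinuation (4.6.2). Two scheduled assessments can reveal it:
- The early CT is due within 7 days before Day 1 of Cycle 3. Cycles last 21 days, so this is 14 to 21 days after the Day 1 dose of Cycle 2. If that was the last dose, 90 − 21 = 69 to 90 − 14 = 76 days of the window remain.
- The end-of-induction assessment is 6 to 8 weeks (42 to 56 days) after Day 1 of the last cycle. For a patient who receives no further study drug, 90 − 56 = 34 to 90 − 42 = 48 days remain.

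**3. Weight of one patient.** Enrolment at 1 March 2018 was 13 FL (9 in dose escalation) and 23 DLBCL (7 in the run-in) (6.1). One affected patient shifts an incidence by 100/n points:

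| Table | n | Shift (points) |
|---|---|---|
| DLBCL expansion | 23 − 7 = 16 | 6.25 |
| DLBCL run-in | 7 | 14.3 |
| FL expansion | 13 − 9 = 4 | 25.0 |
| FL at RP2D, if pooled as in 6.2 | 6 + 4 = 10 | 10.0 |

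These are enrolled numbers. Section 6.5 analyses patients who never received atezolizumab separately, which would make the triplet denominators smaller and the shifts larger.

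**4. Range under stated assumptions.** The documents give neither the proportion starting new treatment within 90 days nor the event rate on it. Assume 10% to 50% start, and 20% to 60% of those have a Grade 3 or higher event from it. The product is 0.10 × 0.20 = 0.02 to 0.50 × 0.60 = 0.30. For the DLBCL expansion phase:
- expected patients affected: 16 × 0.02 = 0.3 to 16 × 0.30 = 4.8;
- chance of at least one: 1 − 0.98^16 = 28% to 1 − 0.70^16 = 99.7%;
- expected inflation: at most 2 to 30 points, and less where the patient had already had such an event on study treatment.

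The range is too wide to serve as an estimate.

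**The case against.** **Attribution.** A reader might infer that next-line toxicity is counted as triplet toxicity. The documents do not support that. Section 6.5 plans all-cause summaries and attributes nothing to the triplet. The main analysis also contains exposure after 1 March 2018 without atezolizumab, and only the censored analysis has a triplet purpose. What stands is mixing, not misattribution.

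**Deaths.** It would also be wrong to say that deaths on the next regimen inflate the incidence tables as a class. Section 6.5 lists deaths, and Section 5.3.5.8 keeps those due solely to lymphoma off the Adverse Event form.

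**Size.** A reader might try to forecast the inflation from the protocol's median PFS in DLBCL. With exponential PFS and 126 days (4.14 months) of induction, progression would be 1 − 0.5^(4.14/5.6) = 40% to 1 − 0.5^(4.14/1.9) = 78%. This does not carry over. The 1.9 months comes from immature data on obinutuzumab plus polatuzumab, and the 5.6 months from rituximab plus polatuzumab at 2.4 mg/kg. PFS events include deaths, and some patients with radiographic progression may continue treatment (3.1.1). Progression is also not the same as starting a new regimen.

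**Existing safeguards.** Causality is recorded: "causality will be assessed individually for each protocol-mandated therapy". Section 6.5 plans no summary that uses it. Infections and neutropenia are selected adverse events, summarized and listed, so a reader of the listings could examine cases in a 36-patient study. That helps, but it leaves the incidences unchanged. Section 4.4.2 prohibits during the study "Any anti-cancer therapy, approved or investigational, other than intrathecal CNS prophylaxis", yet the schedules record new treatment after discontinuation, and the prohibition does not end adverse event counting.

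**The 90-day visit.** Appendix 1 footnote d and Appendix 2 footnote c limit it to patients who stopped for reasons other than progression; Section 3.1.5 has no such limit. The passages must be reconciled. The 90-day reporting rule has no such exception.

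**Consequences.** RP2D selection rested on toxicities in Cycles 1 and 2, and the sponsor had already judged benefit-risk uncompelling (1.5.1). This lowers the stakes; the final safety tables still need to be interpretable.

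**Conclusion.** The gap is real. Following the plan as written mixes events on next-line treatment into the all-cause incidence tables and into the 1 March 2018 analysis. The direction is upward. The documents do not give the size: they support only the weight of one patient, about 6 points in the DLBCL expansion phase, 14 in the DLBCL run-in and 25 in the FL expansion phase. Those figures assume the enrolled denominators, reporting by phase as Section 6.5 states, and a patient with no other event of the same kind. If FL patients at the RP2D are pooled as Section 6.2 describes, the FL figure is 10 points.

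This is an inexpensive improvement to the reporting of the safety endpoints. It does not show that any particular rate will be materially wrong.

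**What to change.** Keep the full 90-day collection and the all-cause main table. In Section 6.5, for both the main and the 1 March 2018 datasets:

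1. Add a summary limited to events with onset before the first new anti-lymphoma treatment, plus any later event that the investigator relates to a study drug.
2. Tabulate the remaining later events separately, including Grade 3 or 4 infections reported under the 2-year rule.
3. Confirm that the eCRF captures the start date of new anti-lymphoma treatment. The appendices require evaluation every 3 months but do not mention a date, and concomitant medication recording stops at the end of treatment. The summary of changes says survival follow-up was dropped in error from the preceding amendment, so check completeness for patients followed under that version.

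Truncating the main table instead would be debatable: the signal in this study was immune-mediated, and retaining late events would then depend on open-label causality judgements.

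The cost is a short addition to Section 6.5 and one extra set of tables. A late immune event coded as unrelated would be absent from the restricted summary, but would appear in the all-cause and post-switch tables.
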